1 PROTOCOL SYNOPSIS

Population: Healthy males and females with mildly elevated LDL levels

Total number of participants: 14

1.1 Inclusion Criteria

1. Provided voluntary, written, informed consent to participate in study
2. Males and females between 30 and 55 years of age
3. BMI between 20.0 to 29.9 kg/m², inclusive
4. Female participant is not of child-bearing potential, defined as females who have undergone a sterilization procedure (e.g. hysterectomy, bilateral oophorectomy, bilateral tubal ligation, total endometrial ablation)
Or,
Females of child-bearing potential must have a negative baseline urine pregnancy test and agree to use a medically approved method of birth control for the duration of the study. Acceptable methods of birth control include:
 - Non hormonal contraceptives
 - Double-barrier method
 - Intrauterine devices
 - Non-heterosexual lifestyle or agrees to use contraception if planning on changing to heterosexual partner(s)
 - Vasectomy of partner at least 6 months prior to screening
5. Subjects with mid-range (2.5–4.1mmol/L or 100-159 mg/dL) elevated LDL-C levels
6. Agrees to maintain current level of physical activity throughout the study
7. Willingness to complete all questionnaires, records, and diaries and assessments associated with the study and to complete all clinic visits.
8. Healthy as determined by medical history, laboratory results, and as assessed by Qualified Investigator (QI)

1.2 Exclusion Criteria

1. Women who are pregnant, breast feeding, or planning to become pregnant during the course of the trial
2. Women who are menopausal or post-menopausal
3. Currently following a diet (i.e. Ketogenic Diet, low-carbohydrate diet)
4. Subjects with high TSH level (>4.5mU/L) or Self reported pre-existing thyroid condition. Treatment on a stable dose of medication for at least 3 months will be considered by the QI
5. Participants with type I or II Diabetes Mellitus
6. Cancer, except skin cancers completely excised with no chemotherapy or radiation with a follow up that is negative. Volunteers with cancer in full remission for more than five years after diagnosis are acceptable.

7. Participants with previous or current pathology of the pancreas
8. Current or history of Gastroesophageal reflux disease (GERD) or any significant disease of the gastrointestinal tract
9. Self reported hypertension or on hypertensives.
10. Significant cardiovascular event in the past 6 months as assessed by the QI.
11. Major surgery in the past 3 months or individuals who have planned surgery during the course of the trial. Participants with minor surgery will be considered on a case-by-case basis by the QI
12. Gastric bypass surgery
13. Individuals with an autoimmune disease or are immune-compromised
14. Self reported HIV-, Hepatitis B- and/or C-positive diagnosis
15. History of or current diagnosis with kidney and/or liver diseases as assessed by the QI on a case-by-case basis, with the exception of history of kidney stones symptom free for 6 months
16. Self reported medical or neuropsychological condition and/or cognitive impairment that, in the QI's opinion, could interfere with study participation
17. Self reported blood/bleeding disorders as per QI
18. Current use of prescribed medications listed in Section 7.3.1
19. Current use of over-the-counter medications, supplements, foods, and/or drinks listed in Section 7.3.2
20. Alcohol or drug abuse within the last 12 months
21. High alcohol intake (>2 standard drinks per day or >10 standard drinks per week)
22. Clinically significant abnormal laboratory results at screening as assessed by the QI
23. Blood donation 30 days prior to screening, during the study, or a planned donation within 30-days of the last study visit
24. Participation in a clinical research trial within 30 days of study initiation
25. Individuals who are unable to give informed consent
26. Any other active or unstable medical condition, that, in the opinion of the QI, may adversely affect the participant's ability to complete the study or its measures or may pose significant risk to the participant

1.3 Schedule of Assessments

Procedures	Visit 1 Screening	Visit 2 Day 0 (Baseline)	Visit 3–7 Day 28–112 Week 4–16	Visit 8 Day 140 Week 20
Informed consent	X			
Review inclusion/exclusion criteria	X	X		
Review medical history	X			
Review concomitant therapies	X	X	X	X
Vitals: Height*, weight, heart rate, blood pressure *Height will only be measured at visit 1	X	X	X	X
Urine pregnancy test	X	X		X
Physical examination		X		
Blood collection for analysis of: CBC, electrolytes (Na ⁺ , K ⁺ , Cl ⁻ , P), HbA1c, fasting glucose, eGFR, creatinine, AST, ALT, total bilirubin, and TSH *TSH will only be measured at visit 1	X			X
DEXA scan** **DEXA will be measured at Visits, 2, 5 and 8 only		X	X	X
ECG** **ECG will be measured at Visits, 2, 5 and 8 only		X	X	X
Blood Markers: Fasting glucose, HbA1c, C-reactive protein, lipid panel, Free Tri-iodothyronine (T3), ESR		X		X
Lipid Panel	X		X	
Nutritional Counselling [#] and dispense Nic’s Keto Diet e-book #As required, remote Nutritional Counselling will be completed on 3-day food records weekly throughout study period		X		
Daily glucose monitors, and keto monitors Dispensed		X	X	
Daily glucose monitors, and keto monitors Returned			X	X
Food Records Dispensed	X	X	X	
Food Records Returned		X	X	X
Subject Diary Dispensed		X	X	
Subject Diary Returned			X	X
Compliance Calculated			X	X
Adverse Events	X	X	X	X

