7.3.2 Over-the-counter Medications, Supplements and Foods/Drinks

Participants who are currently consuming the following over-the-counter (OTC) Medications, supplement and food/drinks will not be allowed to participate unless willing to undergo a 14-day washout period prior to their baseline visit and agree not to take the supplements during the study. Other OTCs supplement and food/drinks will require a case-by-case assessment by the QI based on dose and/or frequency of use to determine adequate washout.

1. NSAIDs, with the exception of ibuprofen
2. Calcium supplements
3. Protein supplements
4. Orlistat
5. Caffeine supplements
6. Carbohydrate boosting Supplements
7. Exogeneous ketone supplements
8. Supplements known to affect weight and/or fat loss or lipid metabolism, including but not limited to:
 - a. Omega 3 and 6 supplements
 - b. Hemp seed oil supplement
 - c. Flaxseed oil supplement

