9 STUDY ASSESSMENTS

9.1 Visit 1 – Screening (Day -45 to Day -1)*

** At the discretion of the Qualified Investigator, any participants falling outside of the screening window (Day -45 to Day -1) due to scheduling issues will be asked to repeat eligibility/screening procedures prior to baseline visit.*

At screening, an informed consent form will be given to the potential volunteer. They will be required to read the information and will be given the opportunity to seek more information if needed, or have the option to take the consent form home to review prior to making their decision. If agreeable, the volunteer will sign the consent form and receive a duplicate of the signed copy. Once consent has been obtained, the screening visit will proceed following a prior 12-hour fast. Each volunteer will be sequentially assigned a screening number to be entered in the screening and enrollment log.

Screening assessments include:

1. Review of medical history and current health status
2. Assessment of inclusion and exclusion criteria
3. Review of concomitant prescribed and over-the-counter (OTC) medications, supplements, foods, and drinks (concomitant therapies)
4. Urine pregnancy test for female potential participants that are of child-bearing potential
5. Height and weight measurements and BMI calculation (Section 9.5.1)
6. Seated resting blood pressure and heart rate measurements (Section 9.5.2)
7. Collection of fasted blood samples for the analysis of complete blood count (CBC), electrolytes (Na⁺, K⁺, Cl⁻, P), HbA1c, glucose, eGFR, creatinine, AST, ALT, and total bilirubin, lipid panel and TSH level analysis
8. Dispense 3-day food records and instruct participants on completion and provide nutrition counselling

The next visit will be scheduled for potentially eligible participants for their baseline visit.

Reminders for participants prior to their next in-clinic visit:

1. Return to the clinic in a 12-hour fasted state
2. Complete 3-day food records
3. Abide by instructions for medications as per Section 7.3.1 and OTC medications, supplements, and food and drinks as per Section 7.3.2.
4. Maintain similar levels of physical activity

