9.2 Visit 2 – Baseline (Day 0)

Eligible participants will return to the clinic for baseline assessments after a 12-hour fast.

Baseline (Day 0) assessments include:

1. Collection and review of food records
2. Assessment of inclusion and exclusion criteria

3. Physical exam
4. Review of concomitant therapies and adverse events
5. Urine pregnancy test for female potential participants that are of child-bearing potential
6. Weight measurements and BMI calculation (Section 9.5.1)
7. Seated resting blood pressure and heart rate measurements (Section 9.5.2)
8. Total body DEXA scan
9. Collection of fasted blood for analysis of glucose, HbA1c, C-reactive protein, lipid panel, Free tri-iodothyronine (T3), and ESR.
10. Deliver Nutrition Counselling about Nic's Keto Diet (Section 9.7.7)
11. Dispense Nic's Keto Diet e-book
12. Dispense glucose and ketone monitors and instruct participants on their use. First fasted ketone and glucose measure to be taken with monitors during baseline clinic visit.
13. Dispense or assign dates of 3-day food records
14. Dispense participant treatment diary and instruct participants on use

The next visit will be scheduled for day 28.

Reminders for participants prior to their next in-clinic visit:

1. Return to the clinic in a 12-hour fasted state
2. Complete 3- day food records weekly. Weekly records will be reviewed by nutrition team and counselling provided as required.
3. Participants will receive a 2-week follow up email from Nutrition Team (Section 9.7.7).
4. Abide by instructions for medications as per Section 7.3.1 and OTC medications, supplements, and food and drinks as per Section 7.3.2.
5. Complete subject treatment diary
6. Maintain similar physical activity and study diet
7. Monitor glucose and ketones daily

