9.9 Laboratory Analyses

Blood samples will be drawn from the participants at screening (Visit 1), baseline (Visit 2, Day 0), Visit 3, Visit 4, Visit 5, Visit 6, Visit 7, and at the End of Study visit (Visit 8, day 140) as indicated in the schedule of assessments.

Protection of subject confidentiality will extend to all data generated from the assaying of these samples. These samples will be alphanumerically coded and the persons performing the analysis will not be aware of the subject's identity.

At screening (Visit 1), 13 mL of ≥ 12 hours fasted whole blood will be collected in:

1. Two 4mL EDTA vacutainer tubes to generate plasma for:
 - a. CBC analysis (one tube)
 - b. Hb1Ac analysis (one tube)

2. One 5mL SST vacutainer tube to generate serum for:
 - a. Electrolytes (Na⁺, K⁺, Cl⁻, P), lipid profile, fasting glucose, eGFR, creatinine, AST, ALT, TSH, and total bilirubin

At baseline (Visit 2), 13 mL of ≥ 12 hour fasted whole blood will be collected in:

1. Two 4mL EDTA vacutainer tubes to generate plasma for:
 - a. Hb1-Ac (one tube)
 - b. ESR (One Tube)
2. One 5mL SST vacutainer tube to generate serum for:
 - a. Fasting glucose, C-reactive protein, lipid panel, Free T3 (one tube)

At Visit 3, 5 mL of ≥ 12 hour fasted whole blood will be collected in:

1. One 5mL SST vacutainer tube to generate serum for:
 - a. Lipid Panel (one tube)

At Visit 4, 5 mL of ≥ 12 hour fasted whole blood will be collected in:

1. One 5mL SST vacutainer tube to generate serum for:
 - a. Lipid Panel (one tube)

At Visit 5, 5 mL of ≥ 12 hour fasted whole blood will be collected in:

1. One 5mL SST vacutainer tube to generate serum for:
 - a. Lipid Panel (one tube)

At Visit 6, 5 mL of ≥ 12 hour fasted whole blood will be collected in:

1. One 5mL SST vacutainer tube to generate serum for:
 - a. Lipid Panel (one tube)

At Visit 7, 5 mL of ≥ 12 hour fasted whole blood will be collected in:

1. One 5mL SST vacutainer tube to generate serum for:
 - a. Lipid Panel (one tube)

At the end of the study (Visit 8), 17 mL ≥ 12 hour fasted whole blood will be collected in:

1. Three 4mL EDTA vacutainer tubes to generate plasma for:
 - a. CBC analysis (one tube)
 - b. Hb1Ac analysis (one tube)

c. ESR (One Tube)

2. One 5mL SST vacutainer tube to generate serum for:
 - a. Electrolytes (Na⁺, K⁺, Cl⁻, P), fasting glucose, eGFR, creatinine, AST, ALT, CRP, Lipid Panel, Free T3, and total bilirubin (one tube)

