10.1.4 Laboratory Test Abnormalities

The investigator must assess the clinical significance of all abnormal laboratory values as defined by the compendium of normal values for the reference laboratory.

Any treatment emergent abnormal laboratory result which is clinically significant, i.e., meeting one or more of the following conditions, should be recorded as a single diagnosis on the AEs form in the study record:

1. Accompanied by clinical symptoms
2. Leading to interruption or discontinuation of the investigational diet
3. Requiring a change in concomitant therapy

This applies to any protocol and non-protocol specified laboratory result from tests performed after the first day of the investigational diet, which falls outside the laboratory reference range and meets the clinical significance criteria for liver and kidney tests as well as for hematology and clinical chemistry, etc. (i.e. AST and/or ALT > 2 x ULN).

This does not apply to any abnormal laboratory result which falls outside the laboratory reference range but which does not meet the clinical significance criteria or those which are a result of an AE which has already been reported.

Any laboratory result abnormality fulfilling the criteria for a serious adverse event (SAE) should be reported as such, in addition to being reported as an AE in the study record.

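### The safety chemistry panel and CBC have no Day 0 value: their only pre-diet sample is the screening draw, 1 to 45 days before the diet

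*Combined protocol and SAP*

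**What the plan says.** Section 5 names clinical chemistry and hematology as safety outcomes, and Section 11.1 describes a pilot exploring efficacy and safety in 14 people. No comparison group is described.

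Three places agree on timing:
- Section 1.3 marks the row with CBC, electrolytes and "HbA1c, fasting glucose, eGFR, creatinine, AST, ALT, total bilirubin, and TSH" at Visits 1 and 8, with nothing at Visits 2 to 7.
- Section 9.2 lists the Day 0 blood work as "Collection of fasted blood for analysis of glucose, HbA1c, C-reactive protein, lipid panel, Free tri-iodothyronine (T3), and ESR".
- Section 9.9 gives the Day 0 serum tube as "Fasting glucose, C-reactive protein, lipid panel, Free T3 (one tube"), and the two Day 0 EDTA tubes go to HbA1c and ESR.

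The screening window is given as "Visit 1 – Screening (Day -45 to Day -1"). Under Section 9.1, people who fall outside it "will be asked to repeat eligibility/screening procedures prior to baseline visit", so 45 days is the planned maximum. Exclusion 22 uses the screening laboratory results. Section 7.3.2 bars users of listed products "unless willing to undergo a 14-day washout period prior to their baseline visit", and the screening visit ends with a reminder to follow that section before baseline.

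On reporting, Section 10.1.4 covers "Any treatment emergent abnormal laboratory result which is clinically significant", judged against the reference range and clinical-significance conditions. Section 11.3.2 summarises safety laboratories at each measurement point. Section 11.3 defines change from Day 0, but for primary and secondary endpoints.

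**The concern.** Section 11.3 refers the primary and secondary endpoints to Day 0. The schedule also gives heart rate and weight (hence BMI) a Day 0 value. Chemistry and hematology do not get one, and no reason is given. For these tests the two summarised points are screening and Day 140. Anyone asking whether the diet affected liver, kidney, electrolytes or blood counts will compare those two.

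Three things other than the diet can enter that comparison:
- **Elapsed time.** Up to 45 days pass before the diet starts.
- **Selection.** The reference value is also the one used to admit the participant. People admitted partly because that value was acceptable will tend to drift back towards their usual level, which can look like deterioration at Day 140.
- **Washout.** For a participant who stops a listed product after screening, the reference may be an on-product value. Stopping the product could produce a change or hide one.

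With no comparison group and no chemistry or CBC at Visits 3 to 7, nothing else in the schedule separates these from the diet. A Day 0 sample that was not taken cannot be recovered later.

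**Working it through.** **Step 1. Which laboratory tests have a Day 0 value (Sections 1.3, 9.1 to 9.6, 9.9).**

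| Test | Visit 1 | Visit 2, Day 0 | Visits 3–7 | Visit 8 |
|---|---|---|---|---|
| Creatinine, eGFR, AST, ALT, bilirubin, electrolytes | yes | no | no | yes |
| CBC | yes | no | no | yes |
| Fasting glucose, HbA1c | yes | yes | no | yes |
| Lipid panel | yes | yes | yes | yes |
| CRP, ESR, free T3 | no | yes | no | yes |

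Glucose and HbA1c share the safety row but also appear in the Day 0 row, so the gap does not apply to them. TSH is a screening test only and is not at issue.

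**Step 2. Reproduce the plan's blood volume.** The tube counts come from Section 9.9.
- Visit 1: 2 × 4 + 5 = 13 mL
- Visit 2: 2 × 4 + 5 = 13 mL
- Visits 3 to 7: 5 × 5 = 25 mL
- Visit 8: 3 × 4 + 5 = 17 mL
- Total: 13 + 13 + 25 + 17 = 68 mL

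This matches the stated figure of about 68 mL. The total therefore rests on a Day 0 draw with no CBC tube, and the Day 0 tube list assigns none of the missing chemistry tests.

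**Step 3. The pre-diet share of the interval.** Let s be the days from screening to Day 0, from 1 to 45. Visit 8 is on Day 140 ± 3.
- Shortest interval: 137 + 1 = 138 days
- Longest interval: 143 + 45 = 188 days
- Pre-diet share at nominal Day 140 is s / (140 + s): 1/141 = 0.7%, 14/154 = 9.1%, 45/185 = 24.3%
- Largest share, with Visit 8 at its earliest: 45 / (45 + 137) = 45/182 = 24.7%

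**Step 4. Does the washout fall after the screening draw?** The washout runs for 14 days up to baseline, and the instruction is given at screening. A current user who starts it after that visit has an on-product screening value. The order follows from the reminders and is not stated as a rule. It concerns listed-product users only; a non-user can be screened on Day -1 with no washout.

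**Step 5. Can the bias be sized?** It would need the number of product users, the shift per person and its direction, and the within-person variability of each analyte. The documents give none of these, so I give no figure in laboratory units.

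**Step 6. Is there room for the tests at Day 0?** One 5 mL SST tube at Visit 8 carries electrolytes plus "fasting glucose, eGFR, creatinine, AST, ALT, CRP, Lipid Panel, Free T3, and total bilirubin (one tube"). The Visit 2 SST tube already carries glucose, CRP, lipids and free T3. Adding the chemistry makes its list the same as at Visit 8.
- Chemistry added: Visit 2 stays 13 mL, total stays 68 mL
- CBC also added (one 4 mL EDTA tube): Visit 2 = 13 + 4 = 17 mL, total = 68 + 4 = 72 mL. Section 9.9 expects no visit to exceed 18 mL.

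With Day 0 as reference, the interval becomes 137 to 143 days, all of it on the diet.

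**The case against.** The schedule is internally consistent, so this is a design choice, and the study is an uncalculated pilot with descriptive safety reporting. That stands, and it limits how much weight the point can carry.

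A reader might infer that the plan will automatically charge any pre-diet laboratory change to the diet. The documents do not support that:
- Section 10.1.1 has the qualified investigator judge causality on five levels, including unlikely and not related.
- Section 10.1.4 defines a laboratory AE by reference range and clinical significance, not by change from a pre-diet value.
- Section 11.3.2 plans no change score or test for safety laboratories, so the Visit 1 to Visit 8 contrast is one that readers will make, not a planned analysis.

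A reader might also infer that the pre-diet values are generally on-product. Exclusion 19 bars current users and washout is the exception to it, so this applies only to an unknown subset.

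There are partial safeguards. The window is capped. Day 0 includes a physical examination and reviews of eligibility, concomitant therapies and AEs. AEs are split into pre-emergent and post-emergent. Section 9.9 allows extra or repeat samples where needed. Day 140 values can also be read against reference ranges. These narrow the problem to silent laboratory changes, but none gives every participant a Day 0 value.

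Finally, a Day 0 draw removes only the pre-diet part. At least three quarters of the interval (137/182 = 75.3%) would be on the diet in any case, and drift there cannot be separated from the diet.

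**Conclusion.** The point holds as a limit on interpretation. Creatinine, eGFR, AST, ALT, total bilirubin, electrolytes and CBC have no Day 0 value. Their only scheduled pre-diet value is 1 to 45 days old, was used for eligibility, and for some product users may precede washout. Up to 24.7% of the interval can be pre-diet. That is the extreme case; it is 9.1% for someone screened on Day -14 and 0.7% on Day -1, both with Visit 8 on Day 140.

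A change arising before Day 0 could be mistaken for a diet effect or could mask one. The documents do not show that any conclusion would be altered, and they do not allow the bias to be sized. The percentages assume that the visit windows are kept. The washout part also assumes that at least one participant stops a listed product after the screening draw. This is a cheap improvement worth making, not a flaw that invalidates the safety assessment.

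**What to change.** **Chemistry.** In Sections 1.3, 9.2 and 9.9, add creatinine/eGFR, AST, ALT, total bilirubin and electrolytes to the Visit 2 order, run on the 5 mL SST tube already drawn. Blood volumes do not change.

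**Analysis.** In Section 11.3.2, name Day 0 as the pre-diet reference for these analytes and add a descriptive summary of change from Day 0 to Day 140. Leave the AE thresholds in Section 10.1.4 as they are. Exclusion 22 already refers to screening results and needs no change.

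**CBC.** Choose one option and write it down. Either add one 4 mL EDTA tube at Visit 2 and restate the Section 9.9 total as 72 mL, or keep Visit 1 as the stated CBC reference. Moving the reference to Day 0 for all safety laboratories without drawing a CBC that day would leave hematology with no pre-diet reference.

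**Cost.** About 14 extra routine chemistry panels, one per participant, plus up to 14 CBCs if that option is taken, and a small amendment. No extra venipuncture is needed. The report should still say that changes during the 140 diet days cannot be separated from the diet without a comparison group.

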2 LIST OF ABBREVIATIONS

AE	Adverse Event
ALT	Alanine Aminotransferase
AST	Aspartate Aminotransferase
BP	Blood Pressure
BMI	Body Mass Index
CBC	Complete Blood Count
CEA	Carcinoembryonic antigen
Cl	Chloride
CPT	Carnitine Palmitoyl Transferase
CRO	Contract Research Organization
DEXA	Dual Energy X-ray Absorption
DOB	Date of Birth
ECG	Electrocardiogram
EDTA	Ethylenediaminetetraacetic Acid
e.g.	"for example"
ESR	Erythrocyte Sedimentation Rate
et al	"and others"
GCP	Good Clinical Practice
GERD	Gastroesophageal Reflux Disease
HbA1C	Hemoglobin A1C
HDL	High-Density Lipoprotein
HIV	Human Immunodeficiency Virus
HR	Heart Rate
lbs.	Pounds
ICF	Informed Consent Form
ICH	International Conference of Harmonization
IEC	Independent Ethics Committee
IRB	Institutional Review Board
ITT	Intent-to-Treat
kg	Kilogram
LCAD	Long-Chain Acyl Dehydrogenase Deficiency
LDL	Low-Density Lipoprotein
LDL-C	Low-Density Lipoprotein Cholesterol
LOCF	Last Observation Carried Forward
MCAD	Medium-Chain Acyl Dehydrogenase Deficiency
MCH	Mean Corpuscular Hemoglobin
MCHC	Mean Corpuscular Hemoglobin Concentration
MCT	Medium Chain Triglyceride
MCV	Mean Corpuscular Volume
mg/dL	Milligrams per Deciliter
mmol/L	Millimoles per Liter
MMRM	Mixed Model for Repeated Measures
Na	Sodium
OTC	Over-the-Counter
PP	Per Protocol

PSA	Prostate Specific Antigen
QI	Qualified Investigator
RBC	Red Blood Cells
RDW	Red Blood Cell Distribution Width
SAE	Serious Adverse Event
SCAD	Short-Chain Acyl Dehydrogenase Deficiency
SOP	Standard Operating Procedure
SST	Serum Separating Tube
TPD	Therapeutics Products Directorate
TSH	Thyroid Stimulating Hormone
UAT	User Acceptance Testing
ULN	Upper Limit of Normal
US	United States
WBC	White Blood Cell

